10.5 Randomization Procedures

Couples will be randomized (1:1) to receive the combination TAF/EVG vaginal insert either 1 hour or 4 hours before and after coitus.

Couples	Randomization Group
16	1 hour before and 1 hour after coitus
16	4 hours before and 4 hours after coitus

10.6 Participant Accrual, Follow-up and Retention

A sufficient number of couples may be consented and undergo assessment procedures in order to have approximately 32 (16 in each site) evaluable couples, i.e., couples that complete all study visits. All participants that undergo baseline sampling will be included in the analysis. Participants who initiate product use but discontinue the study prior to completion may not re-enroll. If either partner (female or male) discontinues the study early, the couple will be discontinued from the study early. Participants who discontinue the study early may be replaced to reach the target of having approximately 32 couples with complete study data. Replacement participants will be assigned to the same group (1hr or 4hr) as the withdrawn participants to avoid bias.

NOTE: Per Section 10.4, a maximum of 4 couples across the 2 study sites (up to 2 per randomization group) may discontinue the study early without requiring that the participants be replaced while still achieving sufficient power to analyze effect differences per site.

10.7 Data and Safety Monitoring and Analysis

10.7.1 Study Monitoring

DSMB oversight is not planned for this study. The MATRIX Clinical Trials Hub will conduct interim reviews of study progress, including rates of participant accrual, retention, completion of primary and main secondary endpoint assessments, and study or laboratory issues. The ISP will conduct interim review of a closed safety data report. These reviews will take place approximately every

three months, or as needed. At the time of these reviews, or at any other time, the ISP or PSRT may convene a panel (composed of the ISP, PSRT and protocol statistician[s]) to review study findings. This panel may recommend that the study proceed as designed, proceed with design modifications, or be discontinued. Safety monitoring will be done by the PSRT.

10.7.2 Primary Analysis(es)

PK and PD:

PK analysis will include descriptive statistics by sample time point of EVG, TFV, and TAF concentrations for all plasma, CVT, and CVF sample types, in addition to TFV-DP concentrations from CVT samples.

PD endpoints will be summarized using descriptive statistics by time point as well as changes from baseline. Estimates and 95% confidence intervals will be provided.

Comparisons:

- At baseline: Compare the 1-hour pre/post coitus and 4-hour pre/post coitus groups to ensure groups are comparable
- At stage 1 (pre coitus)
 - For the 1-hour group: comparing 5 hours after coitus (6 hours after insert) to the 6 hours after insert at baseline
 - For the 4-hour group: comparing 2 hours after coitus (6 hours after insert) to the 6 hours after insert at baseline
- At stage 2 (post coitus)
 - For the 1-hour group: comparing 7 hours after coitus (6 hours after insert) to the 6 hours after insert at baseline
 - For the 4-hour group: comparing 10 hours after coitus (6 hours after insert) to the 6 hours after insert at baseline

Statistical Analysis plan:

Categorical variables will be summarized by frequencies and percentages. Continuous variables will be summarized by mean (SD) when found normally distributed. Median (IQR) will be used otherwise. Normality will be assessed graphically by Q-Q plots and statistically by Shapiro-Wilk test for normality.

To assess for the comparability between the two groups of the study at baseline, t-test or Mann-Whitney test will be used (based on the normality assumptions) to assess for the differences in continuous variables. Chi-squared test for independence or Fisher's exact test will be used for categorical variables as appropriate.

For the 1-hour pre/post coitus insert group, Paired analysis will be conducted for each endpoint at 6 hours post insert for stage 1 and stage 2 to compare to the baseline separately. For this analysis paired t-test or Wilcoxon signed rank test will be used as appropriate. Similar analysis will be conducted for the 4-hour pre/post coitus insert group.

To assess for the change on TFV-DP and other PK parameters over time, repeated measure ANOVA or Friedman test will be used (based on the normality assumptions) to compare all PK parameters of tissue, blood, or vaginal fluid samples at V3, V6, and V9 for the 1-hour pre/post coitus group and the 4-hour pre/post coitus group separately; pairwise comparison will then be conducted using Bonferroni or Sidak correction as needed.

Finally, Mixed Effect Model will be used to compare the PK parameters between the 1-hour pre/post coitus and 4-hour pre/post coitus groups and within each group compared to baseline.

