7.11 Clinical Evaluations and Procedures

Medical History and Physical Examination

A comprehensive medical history for all participants will be taken at screening, followed by a directed history at all visits they attend thereafter. Participants will be asked about

medications/therapies at every visit they attend, including Visit 1. A full physical examination for female participants and a directed physical examination including genital inspection for male participants will be conducted at screening and will include general appearance and evaluation of body systems as outlined in the MATRIX-004 SSP Manual. A directed physical exam for female participants will be conducted at the enrollment visit and, as clinically indicated, for all participants at all follow-up visits they attend to assess any complaints or symptoms. In addition, vital signs and weight will be checked for all participants at all visits they attend. Height will be measured at screening only. Adverse events will be recorded for all participants at all visits they attend after the start of product use at Visit 2.

Pelvic Examination

Pelvic exams will be performed for female participants using visual inspection of external genitalia and using a speculum for examination of the cervix and vagina. Bimanual exam may be performed as needed (required at Screening Visit). Pelvic exams will be conducted at each visit for PK, PD and subclinical safety specimen collection and as indicated based on participant reports. CVF will be collected using swabs. Further specimen collection procedures will be detailed in the MATRIX-004 SSP Manual. Biopsy areas will be checked for healing at applicable visits and as indicated.

Specimen Collection (CVT, CVF and Blood)

CVT will be obtained at Visits 3, 6 and 9 to assess PK and IHC.

The study site should carefully record the date and time of each collection of blood, CVF, and CVT biopsies. The time of sampling will be based on the time the first sample is taken (when multiple sample types are being collected at a time point, all samples should be collected within a short period). Samples collected outside the sampling windows below will be considered a protocol deviation:

- \pm 1 hour outside of the 6-hour post-dose time point at V2, V5 and V8
- \pm 4 hours outside of the 24-hour post-dose time point at V3, V6 and V9
- \pm 2 days outside of the 7-day post-dose time point at V4, V7 and V10

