7.13 Pharmacokinetics (PK) and Pharmacodynamics (PD)

Table 15: Specimens Collected to Assess Safety, PK and Ex Vivo Antiviral Activity

Study Visit	Specimens collected for PK, PD and subclinical safety – Females only		
	Blood	CVF	CVT
Visit 2	
 • Plasma for PK (pre-dose & 6hr post-dose) • PBMC for TFV-DP (pre-dose) 	
 • CVF for PK (pre-dose & 6hr post-dose) • CVF for PD (pre-dose & 6hr post-dose) 	
Visit 3	
 • Plasma for PK • PBMC for TFV-DP 	
 • CVF for PK • CVF for PD 	
 • 2 BXV for PK • 1 BXV for IHC
Visit 4	
 • Plasma for PK • PBMC for TFV-DP 	
 • CVF for PK • CVF for PD 	
Visits 5 (6hr post-dose)	
 • Plasma for PK 	
 • CVF for PK • CVF for PD 	
Visit 6	
 • Plasma for PK • PBMC for TFV-DP 	
 • CVF for PK • CVF for PD 	
 • 2 BXV for PK • 1 BXV for IHC
Visit 7	
 • Plasma for PK • PBMC for TFV-DP 	
 • CVF for PK • CVF for PD 	
Visit 8 (6hr post-dose)	
 • Plasma for PK 	
 • CVF for PK • CVF for PD 	
Visit 9	
 • Plasma for PK • PBMC for TFV-DP 	
 • CVF for PK • CVF for PD 	
 • 2 BXV for PK • 1 BXV for IHC
Visit 10	
 • Plasma for PK • PBMC for TFV-DP 	
 • CVF for PK • CVF for PD 	

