10.4 Sample Size and Power Calculations

Based on previous findings on the impact of sex on TFV vaginal gel from MTN-011¹⁸ and focusing on observed differences in TFV-DP concentrations in vaginal tissue, we would need about 20 female participants (10 per group) to detect a similar effect size (~65%) with 80% power at a 0.05 significance level. We are planning to enroll 32 couples to complete at least 28 to provide sufficient power to analyze effect differences per site. Altogether, this sample size will provide 80% power to detect a minimum of 55% difference in TFV-DP concentration (effect size) at 5% level of significance.

Qualitative data collection

Up to 40 study participants (6-10 female and 6-10 male per site) will be purposively selected and invited to complete an IDI after V8 but before exiting the study.

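### Section 10.7.2 sets the paired analysis at 6 hours for every endpoint, but tissue and PBMC are not sampled then; the 24-hour tissue TFV-DP tests are not named as the key comparison, and the power in 10.4 is tied to no stated test

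*Protocol*

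**What the plan says.** **Analysis.** Protocol Section 10.7.2 (Primary Analysis(es)) itemises the stage-versus-baseline comparisons, two for stage 1 and two for stage 2. All four are at 6 hours after the insert. For the 1-hour group it then states: "Paired analysis will be conducted for each endpoint at 6 hours post insert for stage 1 and stage 2", each against baseline, and it plans the same for the 4-hour group.

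Later in the same section, TFV-DP and the other PK parameters in tissue, blood or vaginal fluid are compared across V3, V6 and V9 by repeated-measures ANOVA or Friedman test, separately by timing group; "pairwise comparison will then be conducted using Bonferroni or Sidak correction as needed". A mixed model between and within groups follows.

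**Sampling.** Section 7.11 states: "CVT will be obtained at Visits 3, 6 and 9 to assess PK and IHC". It places those three visits at 24 hours post-dose. Table 15 and Appendix I show PBMC pre-dose at Visit 2, then at Visits 3, 4, 6, 7, 9 and 10, and none at the 6-hour draws.

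**Sample size.** Section 10.4 works from an earlier TFV gel study, "focusing on observed differences in TFV-DP concentrations in vaginal tissue". It asks for about 20 women (10 per group) to detect an effect size of about 65% "with 80% power at a 0.05 significance level". It continues: "We are planning to enroll 32 couples to complete at least 28", and gives 80% power for a 55% difference with the planned sample. It names no test, time point, contrast or SD.

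**The concern.** The first half of the analysis section claims to cover every endpoint at a time when two of the four matrices are not collected. One of the two is the tissue that sized the trial. The second half of the section does reach tissue, but through a different procedure, at a different time and under a different alpha rule. Nothing says which result answers the primary objective for tissue TFV-DP.

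The power statement has the same gap: it cannot be matched to any test that 10.7.2 writes out without adding assumptions. If this is left open, the choice of tissue contrast, of pooling or not, and of alpha could be made after the data are seen, and the reported power may not describe the test that is run.

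**Working it through.** **1. Endpoints against the schedule** (Sections 10.2, 7.11 and 7.13; Appendix I)

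| Matrix | Primary concentrations | 6 h sample | 24 h sample |
|---|---|---|---|
| Plasma | TFV, TAF, EVG (3) | V2, V5, V8 | V3, V6, V9 |
| CVF | TFV, TAF, EVG (3) | V2, V5, V8 | V3, V6, V9 |
| Tissue | TFV, TFV-DP, TAF, EVG (4) | none | V3, V6, V9 |
| PBMC | TFV-DP (1) | none | V3, V6, V9 |

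Total 3 + 3 + 4 + 1 = 11. Without a 6-hour sample: 4 + 1 = 5.

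**2. Reproducing the stated power.** Sidedness is not stated, so two-sided tests are assumed. For a paired t-test on n women with standardised mean change d, power = P(|T| > t(1−α/2, n−1)), where T is noncentral t with n−1 degrees of freedom and noncentrality d√n. Reading the effect size as d, with both timing groups pooled and α = 0.05:

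- n = 20, d = 0.65: noncentrality 0.65 × √20 = 2.91, power 78.7% (80% needs n = 21).
- n = 28, d = 0.55: noncentrality 0.55 × √28 = 2.91, power 80.1% (80% needs n = 28).

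Both figures in 10.4 are matched. On the same reading, a between-group t-test gives 28.0% (10 per group, 0.65) and 28.9% (14 per group, 0.55).

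**3. The by-group contrasts that 10.7.2 does plan.** With 28 completers there are 28/2 = 14 women per timing group; with all 32 there are 16. Power for a paired t-test at d = 0.55:

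| n per group | α = 0.05 | α = 0.05/2 | α = 0.05/3 |
|---|---|---|---|
| 14 | 47.8% | 35.2% | 28.8% |
| 16 | 53.9% | 41.1% | 34.4% |

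The standardised change detectable with 80% power is 0.81, 0.91 and 0.97 at n = 14, and 0.75, 0.84 and 0.90 at n = 16. The divisor 3 assumes Bonferroni over all pairs of V3, V6 and V9; the divisor 2 assumes only the two contrasts against V3. The protocol fixes neither.

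**4. Reading the effect as a percent difference.** An SD must then be assumed. One choice is to back-solve it from 10 per group, 65% and 80% power in a two-sample t-test, where the detectable d is 1.325:

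- raw scale: SD = 0.65/1.325 = 0.49
- log scale: SD = −ln(0.35)/1.325 = 1.050/1.325 = 0.79

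For a within-woman contrast, SD of the difference = SD × √(2(1−ρ)). Power for a 55% loss at n = 14 and α = 0.05/3:

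| ρ | log | raw |
|---|---|---|
| 0 | 49% | 60% |
| 0.25 | 63% | 74% |
| 0.5 | 83% | 91% |

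Power reaches 80% at ρ of about 0.34 (raw) or 0.47 (log) with 14 women, and about 0.22 or 0.37 with 16.

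**The case against.** The strongest reply is that tissue TFV-DP is already analysed. The later part of 10.7.2 stands under the same Primary Analysis heading, names TFV-DP first and compares tissue at V3, V6 and V9. V3 belongs to the stage without coitus, so V6 vs V3 and V9 vs V3 are the coitus contrasts, and a mixed model against baseline follows. Blood at those visits can be read to include PBMC. This stands. A reader of the itemised list alone might infer that tissue has no primary contrast or is never tested; the document does not support that.

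The power figure is also not shown to be wrong. If 55% and 65% are percent differences, back-solving an SD from the first calculation and moving to 14 per group gives about 53–54% (raw) or 57–58% (log) for a between-group or a by-group paired test, close to the stated 55%. A reader might infer from step 4 that 80% needs a high within-woman correlation. It does not: low to moderate values suffice, and the raw-scale figures are the more relevant ones because Section 10.7.4 applies no transformation.

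A reader might also count the 6-hour plasma and CVF tests, 6 concentrations × 2 stages × 2 groups = 24 with no stated correction, and take 1 − 0.95^24 = 0.71 as a likely false-positive rate. That figure holds only for independent tests. Here analytes share samples, TFV is formed from TAF, and both stages share one baseline. Multiplicity across PK analytes may also be settled in an analysis plan not shown here.

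None of this removes the mismatch between the 6-hour rule for every endpoint and the sampling schedule, or the absence of a test behind 10.4.

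**Conclusion.** The point holds as a contradiction within 10.7.2 and an untied power statement, not as a missing analysis. The 6-hour paired test cannot be run for 5 of the 11 primary concentrations. Tissue TFV-DP is reached only by the 24-hour by-group tests and the mixed model, which are not reconciled with that rule and not named as the key comparison. This rests on the protocol's text alone.

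The size of the power gap depends on the reading. As a standardised effect with two-sided tests, 10.4 matches a pooled paired contrast that 10.7.2 does not write out; the by-group contrasts with 14 women have 48% unadjusted and 29% at 0.05/3. As a percent difference, the power cannot be confirmed or refuted, because neither the SD nor the within-woman correlation is given. No data are lost either way.

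**What to change.** In 10.7.2:

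- Limit the 6-hour paired comparisons to plasma and CVF.
- Name V6 vs V3 and V9 vs V3 (24 hours, within woman) as the key comparisons for tissue TFV-DP. Compare the other tissue analytes and PBMC TFV-DP at 24 hours as well.
- State whether these contrasts are run by timing group or pooled, and at what alpha.

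In 10.4, restate the power for that contrast with the assumed within-woman SD or correlation, the number of women and the multiplicity correction. If a pooled contrast was assumed, write it into 10.7.2 instead.

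The cost is wording in two sections and no new samples. The drawback is that the restated power may be less favourable. Making the other primary endpoints supportive is optional and not needed for this repair.

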6 STUDY PRODUCT

6.1 Regimen

The product being used in this study is the TAF/EVG Vaginal Insert 20/16 mg. Each insert for vaginal administration contains 20 mg tenofovir alafenamide (TAF) and 16 mg elvitegravir (EVG). At each of the study sites, couples will be randomized (1:1) to receive TAF/EVG vaginal insert either 1 hour or 4 hours before and after vaginal coital activity. Each female participant will self-administer 3 doses of vaginal insert during study participation. At IoR/designee discretion, each stage may be repeated once if the participant is unable to complete the stage as instructed in the protocol. This may include repeat dosing after a minimum 14-day washout period if the participant administers the insert but does not complete the stage.

Figure 2: Study Product Regimen

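### Section 10.7.2 tests each within-group contrast twice, by timing group on complete cases and by mixed model, and names neither as primary; site enters no quantitative analysis

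*Protocol*

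**What the plan says.** Section 10.7.2 (Primary Analysis(es)) prescribes three inferential layers.

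- Within each timing group, paired t or Wilcoxon tests at 6 h compare Stage 1 with Stage 0 and Stage 2 with Stage 0.
- Repeated-measures ANOVA or Friedman tests at V3, V6 and V9 are run "for the 1-hour pre/post coitus group and the 4-hour pre/post coitus group separately", followed by pairwise comparisons with Bonferroni or Sidak correction if needed.
- "Finally, Mixed Effect Model will be used to compare the PK parameters between the 1-hour pre/post coitus and 4-hour pre/post coitus groups", and also within each group against baseline.

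The first bullet of its comparison list is "Compare the 1-hour pre/post coitus and 4-hour pre/post coitus groups to ensure groups are comparable", and t, Mann-Whitney, chi-squared or Fisher tests are assigned to that task.

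Section 10.6 states: "All participants that undergo baseline sampling will be included in the analysis". It also lets up to 4 couples, 2 per timing group, leave early without replacement. Section 10.7.4 rules out imputation of missing values. Section 6.1 places the 1:1 randomization at each site. Section 10.4 explains the enlargement beyond 20 women this way: "We are planning to enroll 32 couples to complete at least 28 to provide sufficient power to analyze effect differences per site".

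**The concern.** When two analyses of the same contrast both stand under a primary heading with no order between them, the reported conclusion can depend on which is quoted. Two further data-driven choices add to this: parametric or rank test according to observed normality, and correction as needed. The by-group tests are also the weaker of the two. They split 28 to 32 women into groups of 14 to 16 and cannot use a woman with an incomplete set of stages. That sits badly with the rule that everyone with baseline sampling is analysed. Finally, a trial sized for per-site effects should say where those effects are estimated, and Section 10.7.2 does not.

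**Working it through.** **Which tests overlap**

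| Layer | Time and visits | By group? | Data needed from a woman |
|---|---|---|---|
| Paired t / Wilcoxon | 6 h: V2, V5, V8 | separately | both stages of the pair |
| RM-ANOVA / Friedman | V3, V6, V9 (24 h) | separately | all three stages |
| Mixed model | not restricted | jointly | any observed stage |

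The first two layers use different samples. Each therefore overlaps with the mixed model, not with the other. Tissue TFV-DP, the sizing endpoint, is biopsied only at V3, V6 and V9, so for it the overlap is the second layer with the third.

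**Reproducing Section 10.4**

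The stated inputs are "about 20 female participants (10 per group) to detect a similar effect size (~65%) with 80% power at a 0.05 significance level" and "80% power to detect a minimum of 55% difference in TFV-DP concentration (effect size) at 5% level of significance", the latter with 28 completers. Neither SD nor sidedness is given. I read 65% and 55% as standardised effects d (assumption) and used a two-sided paired t-test pooled over both timing groups, with noncentrality d√n and n − 1 df.

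- d = 0.65, n = 20: 0.65 × √20 = 2.907, power 78.7% (n = 21 gives 80.9%).
- d = 0.55, n = 28: 0.55 × √28 = 2.910, power 80.1%.

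Both figures reproduce closely. A second reading also fits: a two-sample t-test with 10 and 14 per group needs d = 1.325 and 1.100, which match 65% and 55% if the SD is about half the mean (0.65/1.325 = 0.49; 0.55/1.100 = 0.50). That is a comparison of 1 h with 4 h, which only the mixed model makes after baseline. On neither reading does the stated power belong to the by-group tests.

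**Power of the by-group tests (paired reading, d = 0.55)**

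- n = 14: 0.55 × √14 = 2.058, power 47.8%.
- n = 16: 0.55 × 4 = 2.200, power 53.9%.
- With Bonferroni over three pairwise tests: 28.8% and 34.4%.
- Effect detectable with 80% power at n = 14: d = 0.81.

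**Partial data**

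Up to 32 − 28 = 4 couples, 4/32 = 12.5%, may leave unreplaced. I compared generalised least squares on all observed stages with complete triples, taking 14 complete women and 2 dropouts per group, compound symmetry, and correlation ρ assumed between 0.2 and 0.8.

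- Both dropouts leave after Stage 1: variance ratio for Stage 1 vs 0 is 14/16 = 0.875, a 12.5% saving.
- Both leave after Stage 0, ρ = 0.8: ratio 0.9875, a saving of about 1%.

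The range is about 1% to 13%. The upper end concerns the tests needing triples; a paired 6 h test keeps a woman who has both stages of that pair.

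**Baseline comparability test**

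Two-sample t, 16 per group: for a 0.5 SD difference the noncentrality is 0.5 × √(16/2) = 1.414 and power is 27.8%. For 0.8 SD it is 59.1%.

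**Value of a common Stage 0 mean**

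Stage 0 is dosing without coitus, the same condition in both groups. Under compound symmetry:

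- Within-group contrast: variance factor (3 + ρ)/4 = 0.80, 0.875, 0.95 at ρ = 0.2, 0.5, 0.8.
- 1 h vs 4 h, against change scores: (1 + ρ)/2 = 0.60, 0.75, 0.90.

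**The case against.** The strongest defence is that the planned mixed model already supplies what is wanted, and that covariates, covariance structure and ranking may sit in a SAP that is not shown. Much of this stands, and it rules out several stronger readings.

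- *That each contrast is tested three ways.* It is tested two ways, because the paired tests and the ANOVA/Friedman tests use different time points.
- *That the include-all rule is contradicted outright.* The rule speaks of the analysis, not of every test, and the mixed model and descriptive summaries can use partial data. The tension is confined to the by-group tests.
- *That Stage 0 is ignored.* It is the comparator in every layer. What is missing is any statement that it is a common baseline for both groups.
- *That site is excluded.* The mixed model's covariates are simply not listed. A site main effect also cancels from a within-woman contrast.
- *That baseline adjustment would cut the variance of the 1 h vs 4 h comparison by up to 49%.* The factor 1 − ρ² (25% at 0.5, 49% at 0.7) is relative to a post-only comparison that the plan does not state. Against change scores the saving is 25% at 0.5 and 15% at 0.7.
- *That pooling the groups shows a 29% loss of precision.* The smaller SE (1/√2) belongs to an effect averaged over both groups, a different estimand.

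The 12.5% dropout is also a ceiling: Section 10.6 allows replacement and Section 5.1.2 targets 95% retention.

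The defence does not answer two points. The protocol itself places overlapping analyses under its primary heading without a lead, and it justifies the sample size by site effects while mentioning site comparison only in the qualitative analysis (Section 10.7.3).

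**Conclusion.** The point holds at moderate weight. Each within-group contrast has two primary-labelled tests and no lead. The by-group tests use 14 to 16 women and lose partial data at a variance cost of about 1% to 13%, given compound symmetry and assumed correlations of 0.2 to 0.8. Their power is about 48% to 54%, against the 80% stated, if the 55% is a standardised paired effect; that reading is an assumption, supported only by its reproducing the sample sizes.

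A reader might infer that a joint model restores 80% power to each by-group contrast. It does not: the 80% at n = 28 is for an effect pooled over timing groups, and a common Stage 0 mean reduces within-group variance by only about 5% to 20%. The same limit applies by site. An even split of 28 completers gives 14 per site, hence about 48% on the same reading.

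The baseline significance test cannot ensure comparability, and a non-significant result should not be read that way.

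**What to change.** In Section 10.7.2, name the planned mixed model as the single primary analysis for each analyte and time point. Specify stage, timing group by stage for Stages 1 and 2, Stage 0 as a common baseline for both groups, site, and a random effect for woman, using all observed stages. Read the Stage 1 vs 0, Stage 2 vs 0 and 1 h vs 4 h contrasts from it. Make the paired and ANOVA/Friedman tests supportive, and replace the baseline significance tests with descriptive summaries.

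In Section 10.4, state which contrast the 80% power refers to, with the SD and sidedness. Either add a stage-by-site estimate or withdraw the claim of sufficient power per site.

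If a log scale is wanted, first reconcile it with Section 10.7.4, which applies no transformation and sets values below detection to 0, where a log is undefined.

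The cost is protocol and SAP wording; site and Stage 0 values are already collected. The price in assumptions is a common residual variance and a common Stage 0 mean across the randomized groups. The supportive by-group tests offer a check on the first.
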